## Laboratory Values: Hematology

Parameter	Grade 1 Mild	Grade 2 Moderate	Grade 3 Severe	Grade 4 Potentially Life-Threatening
Absolute CD4+ Count, Low (cell/mm  ; cells/L) (not HIV infected)	300 to <400 300 to <400	200 to <300 200 to <300	100 to <200 100 to <200	<100 <100
Absolute Lymphocyte Count, Low (cell/mm  ; cells/L) (not HIV infected)	600 to <650 0.600 × 10^9 to <0.650 × 10^9	500 to <600 0.500 × 10^9 to <0.600 × 10^9	350 to <500 0.350 × 10^9 to <0.500 × 10^9	<350 <0.350 × 10^9
Absolute Neutrophil Count (ANC), Low (cells/mm  ; cells/L)	800 to 1,000 0.800 × 10^9 to 1.000 × 10^9	600 to 799 0.600 × 10^9 to 0.799 × 10^9	400 to 599 0.400 × 10^9 to 0.599 × 10^9	<400 <0.400 × 10^9
Fibrinogen, Decreased (mg/dL; g/L)	100 to <200 1.00 to <2.00 OR 0.75 to <1.00 × LLN	75 to <100 0.75 to <1.00 OR ≥0.50 to <0.75 × LLN	50 to <75 0.50 to <0.75 OR 0.25 to <0.50 × LLN	<50 <0.50 OR <0.25 × LLN OR Associated with gross bleeding
Hemoglobin o, Low (g/dL; mmol/L) p ≥13 years of age; male only	10.0 to 10.9 6.19 to 6.76	9.0 to <10.0 5.57 to <6.19	7.0 to <9.0 4.34 to <5.57	<7.0 <4.34
Hemoglobin p, Low (g/dL; mmol/L) p ≥13 years of age; female only	9.5 to 10.4 5.88 to 6.48	8.5 to <9.5 5.25 to <5.88	6.5 to <8.5 4.03 to <5.25	<6.5 <4.03
INR, High (not on anticoagulation therapy)	1.1 to <1.5 × ULN	1.5 to <2.0 × ULN	2.0 to <3.0 × ULN	≥3.0 × ULN
Methemoglobin (% hemoglobin)	5.0 to <10.0%	10.0 to <15.0%	15.0 to <20.0%	≥20.0%
PTT, High (not on anticoagulation therapy)	1.1 to <1.66 × ULN	1.66 to <2.33 × ULN	2.33 to <3.00 × ULN	≥3.00 × ULN
Platelets, Decreased (cells/mm  ; cells/L)	100,000 to <125,000 100,000 × 10^9 to <125,000 × 10^9	50,000 to <100,000 50,000 × 10^9 to <100,000 × 10^9	25,000 to <50,000 25,000 × 10^9 to <50,000 × 10^9	<25,000 <25,000 × 10^9
PT, High (not on anticoagulation therapy)	1.1 to <1.25 × ULN	1.25 to <1.50 × ULN	1.50 to <3.00 × ULN	≥3.00 × ULN
WBC, Decreased (cells/mm  ; cells/L)	2,000 to 2,499 2,000 × 10^9 to 2.499 × 10^9	1,500 to 1,999 1,500 × 10^9 to 1,999 × 10^9	1,000 to 1,499 1,000 × 10^9 to 1,499 × 10^9	<1,000 <1,000 × 10^9

Abbreviations: HIV = human immunodeficiency virus; INR = international normalized ratio; LLN = lower limit of normal; PT = prothrombin time; PTT = partial thromboplastin time; WBC = white blood cell; ULN = upper limit of normal.

- o. Male and female sex are defined as sex at birth. For transgender subjects who have been on hormone therapy for more than 6 consecutive months, grade hemoglobin based on the gender with which they identify (ie, a transgender female should be graded using the female sex at birth hemoglobin laboratory values).
- p. The most commonly used conversion factor to convert g/dL to mmol/L is 0.6206. For grading hemoglobin results obtained by an analytic method with a conversion factor other than 0.6206, the result must be converted to g/dL using appropriate conversion factor for the particular laboratory.

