## **8.6. Dose Modification due to Adverse Events**

The dose of Peg-IFN $\alpha$  may be adjusted due to AEs. Where dose adjustment is required for moderate to severe adverse reactions (clinical and/or laboratory) initial dose reduction to 135  $\mu$ g is generally adequate for patients. In some cases, dose reduction to 90  $\mu$ g or 45  $\mu$ g is necessary. Dose increases to or towards the original dose may be considered when the adverse reaction abates. Details of recommended dose reductions of Peg-IFN $\alpha$  are provided in the package insert for the commercially available product used in this study.

There is no dose modification allowed for 731 or ETV.

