### **7.2.1.       Graded Laboratory Values**

The criteria specified in the study protocol will be used to grade laboratory results as normal (no grade), mild (Grade 1), moderate (Grade 2), severe (Grade 3) or potentially life threatening (Grade 4). See Appendix 3 of the protocol for detailed DAIDS grading criteria on the relevant laboratory tests. For laboratory tests with criteria for both increased and decreased levels, analyses for each direction (i.e., increased, decreased) will be presented separately.

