#### **7.2.1.1.      Treatment-Emergent Laboratory Abnormalities**

Treatment-emergent laboratory abnormalities are defined as values that increase at least 1 toxicity grade from Baseline at any postbaseline time point, up to and including the date of last dose of any study drug plus 28 days for the Overall Treatment Phase. For the Randomized Treatment Phase, the treatment-emergent laboratory abnormalities will be summarized up to the last dose at Week 24.

If the relevant baseline laboratory value is missing, any abnormality of at least Grade 1 observed within the time frame specified above will be considered treatment emergent.

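### In the haematology toxicity table, all platelet limits and all but one WBC limit in cells/L are printed 1,000-fold higher than the cells/mm³ limits beside them, and the SAP does not say which unit is used for grading.

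*Combined protocol and SAP*

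**What the plan says.** The platelet and WBC rows of Protocol Appendix 3 (Laboratory Values: Hematology) are labelled as giving limits in cells/mm³ and in cells/L.

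- Platelets, Grade 1 begins "100,000 to <125,000 100,000 × 10 9"; Grade 4 is "<25,000 <25,000 × 10 9".
- WBC, Grade 1 is "2,000 to 2,499 2,000 × 10 9 to 2.499 × 10 9"; Grade 4 is "<1,000 <1,000 × 10 9".

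In each, the per-mm³ figures come first and the per-litre figures follow; the trailing 9 is the exponent of 10⁹.

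The table is operative. Protocol 8.2 has investigators grade laboratory abnormalities by Appendix 3. SAP 7.2.1 says "The criteria specified in the study protocol will be used to grade laboratory results" and points to the same appendix. SAP 7.2.1.1 defines a treatment-emergent laboratory abnormality by "values that increase at least 1 toxicity grade from Baseline at any postbaseline time point". Neither SAP section gives the unit in which platelets or WBC are graded. The eligibility floors in Protocol 5.3 are in /mm³: 100,000 for platelets and 2,500 for WBC.

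**The concern.** The two sets of limits in one table cell should describe the same count. For platelets and WBC they do not, so the grade a subject receives depends on which unit the programmer uses, and the plan does not say which. WBC Grade 1 in cells/L, "2,000 × 10 9 to 2.499 × 10 9", runs from a larger number to a smaller one, so no value can fall in it.

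Abnormal laboratory results are part of the primary endpoint (Protocol 3.2.1). Protocol 2.1 lists cytopenias among the common side effects of interferon, and two of the three arms receive Peg-IFNα. At stake are the graded platelet and WBC summaries in SAP 7.2.1.2. With per-litre limits taken literally, the treatment-emergent counts for these two tests would carry no information, and the maximum-grade table would show Grade 4 for everyone tested.

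**Working it through.** **Conversion.** 1 L = 10⁶ mm³, so cells/L = cells/mm³ × 10⁶. Expressed in 10⁹/L, this is the cells/mm³ figure divided by 1,000. All limits below are as printed in Appendix 3.

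| Row | Limit, cells/mm³ | Correct, × 10⁹/L | Printed, × 10⁹/L | Printed ÷ correct |
|---|---|---|---|---|
| Lymphocytes | 600 | 0.600 | 0.600 | 1 |
| ANC | 800 | 0.800 | 0.800 | 1 |
| Platelets | 125,000 | 125 | 125,000 | 1,000 |
| Platelets | 100,000 | 100 | 100,000 | 1,000 |
| Platelets | 50,000 | 50 | 50,000 | 1,000 |
| Platelets | 25,000 | 25 | 25,000 | 1,000 |
| WBC | 2,499 | 2.499 | 2.499 | 1 |
| WBC | 2,000 | 2.000 | 2,000 | 1,000 |
| WBC | 1,999 | 1.999 | 1,999 | 1,000 |
| WBC | 1,500 | 1.500 | 1,500 | 1,000 |
| WBC | 1,499 | 1.499 | 1,499 | 1,000 |
| WBC | 1,000 | 1.000 | 1,000 | 1,000 |

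Each row of the toxicity table has seven limits across its four grades, and some values serve two adjacent grades. Counting all seven, the ratio is 1,000 for 7 of 7 platelet limits and 6 of 7 WBC limits. It is 1 for all seven ANC and all seven lymphocyte limits.

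**Grading the same count in both units, limits taken literally.**

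| Count, cells/mm³ | Same count, × 10⁹/L | Grade by mm³ limits | Grade by printed per-litre limits |
|---|---|---|---|
| Platelets 450,000 | 450 | none | 4 |
| Platelets 150,000 | 150 | none | 4 |
| Platelets 100,000 (eligibility floor) | 100 | 1 | 4 |
| Platelets 40,000 | 40 | 3 | 4 |
| WBC 10,000 | 10 | none | 4 |
| WBC 4,000 | 4 | none | 4 |
| WBC 2,500 (eligibility floor) | 2.5 | none | 4 |
| WBC 1,200 | 1.2 | 3 | 4 |

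To escape Grade 4 on the printed per-litre limits, a subject would need:

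- platelets of at least 25,000 × 10⁹/L = 25,000,000/mm³, which is 250 times the eligibility floor (25,000,000 ÷ 100,000);
- WBC of at least 1,000 × 10⁹/L = 1,000,000/mm³, which is 400 times the eligibility floor (1,000,000 ÷ 2,500).

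**Treatment-emergent rule (SAP 7.2.1.1).** Take a platelet fall from 200,000 to 60,000/mm³. By the mm³ limits it goes from no grade to Grade 2 and is treatment-emergent. By the printed per-litre limits it is 200 to 60 × 10⁹/L, Grade 4 to Grade 4, and is not counted. Grade 4 is the top of the scale, so no later value can rise by one grade. The exception is a subject with a missing baseline: SAP 7.2.1.1 then counts any value of Grade 1 or above, and under this reading even a normal count would enter as Grade 4.

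**The case against.** The strongest reply is that nothing in the documents shows the per-litre limits being used. The cells/mm³ limits are printed first, are internally consistent, and are in the unit of the eligibility criteria. A programmer who grades in cells/mm³ gets correct results, and a table with every subject at Grade 4 on two tests would probably be noticed. This stands: the harm is conditional.

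It may also be a punctuation error. If the commas in the per-litre entries are read as decimal points, every disputed limit becomes correct, and the comma and point together in WBC Grade 1 fit that explanation. Reading the PDF by program could also have produced it. Against this, decimal points survive in the ANC and lymphocyte rows and in 2.499 itself, and the comma is a thousands separator in the per-mm³ half of the same cells. The CD4 row also repeats its per-mm³ numbers under cells/L; CD4 is not among the study's tests (Appendix 2, Table 2), so nothing follows for the analysis. An extraction fault is less likely but not excluded.

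Two stronger readings are tempting, and the documents support neither.

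- A reader might infer that no treatment-emergent cytopenia could be recorded. The ANC and lymphocyte rows convert correctly and haemoglobin does not use these units. A clinically significant fall in platelets or WBC is still reported as an adverse event (Protocol 8.5). Protocol 10.3.6.2 also classifies results by laboratory reference ranges, and SAP 7.2 plans quantitative summaries, so the fall would remain visible.
- A reader might infer that Peg-IFNα dosing would go wrong, because Protocol 8.6 reads "Where dose adjustment is required for moderate to severe adverse reactions (clinical and/or laboratory". That section does not cite Appendix 3 grades and refers the details to the package insert. No dosing consequence follows from the table.

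**Conclusion.** The contradiction holds as printed: 13 of 14 platelet and WBC limits in cells/L exceed their own cells/mm³ limits by a factor of 1,000, and the WBC Grade 1 range in cells/L is empty. These are limits that investigators and the SAP are told to use, so this is more than a background typo.

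The effect on results is narrow and conditional. It arises only if grading is run literally on the per-litre limits, and it then affects the graded summaries of two tests, for all of the approximately 60 planned subjects who are tested. If grading uses the cells/mm³ limits, or a correct conversion of them, the effect is nil. The conclusion assumes that the printed page matches the text read here, and that no subject's count approaches 25,000,000 platelets or 1,000,000 white cells per mm³.

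**What to change.** 1. Look at the Appendix 3 page in the protocol PDF to see whether the commas are in the source or came from text extraction. If the source has decimal points, no table correction is needed.
2. If the source matches the text, make the eight cells/L entries agree with the table's own cells/mm³ limits. No threshold changes:
   - Platelets, Grades 1 to 4: 100 to <125, 50 to <100, 25 to <50, and <25 × 10⁹/L.
   - WBC, Grades 1 to 4: 2.000–2.499, 1.500–1.999, 1.000–1.499, and <1.000 × 10⁹/L.
3. State in SAP 7.2.1 that platelets and WBC are graded on the cells/mm³ limits or their correct conversion. The study has been terminated and the SAP finalized, so the Synoptic CSR can carry the statement; SAP Section 1 already sends later changes there.
4. Confirm which unit the grading program used. If it used the printed per-litre limits, rerun the graded platelet and WBC tables.

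The cost is one page check, up to eight table cells and one sentence; a rerun of two tests is needed only if the wrong limits were applied.

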### Laboratory Values: Urinalysis

Parameter	Grade 1 Mild	Grade 2 Moderate	Grade 3 Severe	Grade 4 Potentially Life-Threatening
Glycosuria (random collection tested by dipstick)	Trace to 1+ or $\leq 250$ mg	2+ or $>250$ to $\leq 500$ mg	$>2+$ or $>500$ mg	NA
Hematuria (not to be reported based on dipstick findings or on blood believed to be of menstrual origin)	6 to $<10$ RBCs per high power field	$\geq 10$ RBCs per high power field	Gross, with or without clots OR with RBC casts OR Intervention indicated	Life-threatening consequences
Proteinuria (random collection tested by dipstick)	1+	2+	3+ or higher	NA

Abbreviations: NA = not applicable; RBC = red blood cells.

## **APPENDIX 4 PREGNANCY PRECAUTIONS AND THE DEFINITION OF CHILDBEARING POTENTIAL AND CONTRACEPTIVE REQUIREMENTS**

### **Pregnancy Precautions**

Embryofetal development studies with 731 have not been conducted in animals, therefore effects of 731 on pregnancy are unknown. Contraceptive requirements for female subjects of childbearing potential are required as described below. Contraceptive requirements for ETV and Peg-IFN $\alpha$  are described in the respective package inserts.

### **Definition of Female Subjects of Childbearing Potential**

A female subject is considered of childbearing potential following menarche and until becoming postmenopausal unless permanently sterile (see below).

If fertility is unclear (eg, amenorrhea in adolescents or athletes) and a menstrual cycle cannot be confirmed before first dose of study drug, additional evaluation should be considered.

Female subjects in the following categories are not considered of childbearing potential

Premenopausal with one of the following:

- Documented hysterectomy
- Documented bilateral salpingectomy
- Documented bilateral oophorectomy

Postmenopausal: A postmenopausal state is defined as no menses for 12 months without an alternative medical cause.

A high FSH level in the postmenopausal range may be used to confirm a postmenopausal state in women not using hormonal contraception or hormonal replacement therapy (HRT). However, in the absence of 12 months of amenorrhea, confirmation with more than 1 FSH measurement is required.

Females on HRT and whose menopausal status is in doubt will be required to use one of the non-estrogen hormonal highly effective contraception methods if they wish to continue their HRT during the study. Otherwise, they must discontinue HRT to allow confirmation of postmenopausal status before study enrollment.

For individuals with permanent infertility due to an alternate medical cause other than the above, (eg, Müllerian agenesis, androgen insensitivity), Investigator discretion should be applied to determining study entry.

Documentation to determine childbearing potential can come from the site personnel's review of the subject's medical records, medical examination, or medical history interview.

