## 5.2. Inclusion Criteria

Subjects must meet all of the following inclusion criteria in order to be eligible for enrollment:

1. Willing and able to provide informed consent
2. Male or female between the ages 18 and 65 years (inclusive)
3. Body mass index (BMI) 18 to 36 kg/m^2 and a minimum body weight of 45 kg (inclusive)
4. Female subjects must be non-pregnant and have a negative serum pregnancy test at Screening and a negative urine pregnancy test predose on Day 1
5. Chronic hepatitis B infection, defined as HBV infection for  $\geq$ 6 months documented, for example, by at least 2 measurements of HBsAg positivity and/or detectable HBV DNA  $\geq$ 6 months apart (inclusive of Screening). For subjects without clear documentation of CHB, serum immunoglobulin M (IgM) antibody to the HBV core antigen (HBcAb) must be negative at Screening to exclude acute HBV infection.
6. HBeAg positive with HBV DNA  $\geq 2 \times 10^4$  IU/mL at Screening
7. Lack of cirrhosis or advanced liver disease as documented by the following:
  - Liver biopsy results demonstrating absence of cirrhosis (eg, METAVIR F0-F3 or equivalent) within 1 year of Screening

OR

  - Fasting FibroScan®  $\leq 12$  kPa within 3 months of Screening (including the Screening visit) or other Sponsor-approved hepatic imaging method within 6 months of Screening indicating lack of cirrhosis (eg, F0-F3 or equivalent)

If the results from both liver biopsy and FibroScan are available, then the diagnostic method reporting the most advanced liver disease will be used to determine eligibility for the study
8. A candidate for interferon-based therapy
9. Agreement to comply with protocol-specified contraceptive requirements ([Appendix 4](#))
10. Agreement to abstain from alcohol abuse (defined as alcohol consumption exceeding 2 standard drinks per day on average [1 standard drink = 14 grams of alcohol]) and the use of illicit substances from Screening through the duration of the study
11. In good general health, except for CHB, in the opinion of the Investigator
12. Have the ability to take oral medication, be willing to receive subcutaneous injections of Peg-IFN $\alpha$  (if applicable), and in the opinion of the Investigator, be willing to adhere to study treatment and procedures

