### **6.6.1. Prohibited Concomitant Therapy**

Systemic (oral, injectable, or implanted) hormonal birth control is not considered as an acceptable means of contraception for female subjects of child-bearing potential. Additional details on acceptable means of contraception are provided in [Appendix 4](#).

Other treatments for CHB as defined in Exclusion Criterion #1, [Section 5.3](#) are prohibited.

Since 731 is a weak inhibitor of cytochrome P450 (CYP) 2C9, concomitant use with narrow index CYP2C9 substrates such as warfarin and phenytoin are prohibited. Use of other CYP2C9 substrates should be avoided. Those taking sulfonylureas for controlled diabetes mellitus should monitor blood sugar levels and adjust dosage as appropriate. To the extent possible, other medications with narrow therapeutic indices should be avoided. The route of elimination of 731 in humans is not fully understood so inhibitors and inducers of CYP3A4 should be avoided. Examples of representative medications that should be avoided due to drug-drug interaction potential with 731 is provided in [Appendix 5](#). The designated Medical Monitor may be consulted for any questions regarding acceptable

or prohibited concomitant medication use during the study. As previously described, concomitant medications, over-the-counter medications, and supplements must be recorded in the subject's source documentation.

The details of permitted concomitant medications and prohibited medications for ETV and Peg-IFN $\alpha$  are provided in the respective package inserts for the commercially available products used in this study.

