### **Contraceptive Requirements**

Note that the drug-drug interaction of 731 and systemic (oral/injectable/implantable) hormonal birth control has not been assessed; therefore, systemic hormonal birth control is not considered an effective birth control method for female subjects for the purposes of this study.

Female subjects of childbearing potential (defined above) must agree to use dual effective birth control methods for the duration of the study including the follow-up period. Effective birth control methods include male or female condom (may not be used together due to increased risk of breakage), vasectomy, tubal sterilization, intrauterine device (IUD), diaphragm, or cervical cap. Female subjects must have a negative serum pregnancy test at Screening and a negative urine pregnancy test prior to receiving the first dose of study drug at Baseline (Day 1).

All male subjects must agree to use dual effective birth control methods with their female partners if they are of childbearing potential for the duration of the study including the follow-up period. In this case, effective birth control methods include systemic (oral/injectable/implantable) hormonal birth control, male or female condom (may not be used together due to increased risk of breakage), vasectomy, tubal sterilization, IUD, diaphragm, or cervical cap. Male subjects must avoid sperm donation from the time of the first dose of study drug and throughout the study period, and for at least 30 days after administration of the last dose of study drug.

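### Appendix 4 gives women who continue HRT with doubtful menopausal status a one-method instruction from an unlisted set, at odds with the protocol's dual-method rule

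*Combined protocol and SAP*

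**What the plan says.** Three places in the protocol bear on the same woman.

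- **Appendix 4, Definition of Female Subjects of Childbearing Potential.** The default is: "A female subject is considered of childbearing potential following menarche and until becoming postmenopausal unless permanently sterile". A woman on HRT whose menopausal status is in doubt, and who wishes to continue HRT, "will be required to use one of the non-estrogen hormonal highly effective contraception methods". The alternative follows at once: "Otherwise, they must discontinue HRT to allow confirmation of postmenopausal status before study enrollment".
- **Appendix 4, Contraceptive Requirements.** "Female subjects of childbearing potential (defined above) must agree to use dual effective birth control methods", for the whole study including follow-up. The accepted methods for female subjects are a male or female condom, "vasectomy, tubal sterilization, intrauterine device (IUD), diaphragm, or cervical cap". Because the interaction of 731 with oral, injectable or implantable hormonal contraception has not been assessed, "systemic hormonal birth control is not considered an effective birth control method for female subjects for the purposes of this study".
- **Section 6.6.1, Prohibited Concomitant Therapy.** The same exclusion stands in the protocol body: systemic "hormonal birth control is not considered as an acceptable means of contraception for female subjects of child-bearing potential".

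Appendix 4 is tied to entry by Inclusion Criterion 9 in Section 5.2: "Agreement to comply with protocol-specified contraceptive requirements". Section 7.1 allows no waivers.

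**The concern.** The HRT sentence asks for one method, and the general rule asks for two. The HRT sentence takes its method from a class called highly effective. That term appears nowhere else in Appendix 4, and the general list is labelled only as effective. On one reading, the class is also largely one that the protocol refuses to count.

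What is at stake is subject safety, not inference. The Pregnancy Precautions paragraph of Appendix 4 states that no animal embryofetal development studies of 731 have been done and that its effects on pregnancy are unknown. Contraception is the control that acts before conception; pregnancy tests and the stopping rules act afterwards. Sample size, endpoints and analyses are untouched.

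**Working it through.** No arithmetic applies. The check sets the rules side by side and asks which choices satisfy both.

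**Step 1: do both rules cover the same woman?** Yes. She has not been shown to be postmenopausal or permanently sterile, so the default definition keeps her of childbearing potential. The appendix offers FSH confirmation only to women not using hormonal contraception or HRT, so continuing HRT closes that route. The age limit of 65 and the absence of any named ban on HRT in Section 6.6.1 mean that she can enrol.

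**Step 2: compare the rules.**

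| Feature | HRT sentence | Contraceptive Requirements |
|---|---|---|
| Number of methods | one | two |
| Label | highly effective | effective |
| Methods listed | none | condom, vasectomy, tubal sterilization, IUD, diaphragm, cervical cap |
| Systemic hormonal | depends on the reading | not counted (also Section 6.6.1) |

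**Step 3: the two readings of the HRT phrase.**

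- Reading A: hormonal methods that contain no estrogen, such as systemic progestin-only products. This conflicts on number and largely on type. A hormonal IUD is the one hormonal option left open, because only systemic methods are excluded and IUDs are listed without qualification.
- Reading B: any method other than estrogen-hormonal ones. The type conflict eases. The mismatch of one against two and the unlisted set remain.

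**Step 4: test some choices.** The protocol does not define the highly effective tier, so the middle column assumes that IUDs and progestin-only products belong to it.

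| Choice | Meets HRT sentence? | Meets Contraceptive Requirements? |
|---|---|---|
| Hormonal IUD plus condom | yes, A or B | yes |
| Non-hormonal IUD plus condom | B only | yes |
| IUD alone | yes (hormonal: A or B; non-hormonal: B) | no, one method |
| Progestin-only injection alone | yes, A or B | no, none that counts |
| Progestin-only injection plus condom | yes, A or B | no, only the condom counts |
| Condom plus diaphragm | cannot be determined | yes |

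Some choices meet both rules, so the two can be applied together. Others meet the HRT sentence and fail the general rule, and a site relying on that sentence alone would not see the failure. The last row shows that even a site applying the dual-method rule cannot tell whether the HRT sentence is met.

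**Step 5: which rule governs?** Pregnancy Precautions points forward to the requirements set out below it, Inclusion Criterion 9 requires agreement to them, and waivers are excluded. The dual-method rule therefore binds. Nothing in the HRT sentence says so.

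**The case against.** The strongest reply is that this is a missing cross-reference. The HRT sentence sits under a definition heading and the operative rule follows in the next subsection. The rules can be cumulative, since a woman using two methods can also be using one from the special class. The type conflict exists on one reading only, and Section 6.6.1 repeats the systemic exclusion and offers the Medical Monitor for questions. Harm needs a rare subject at a site that takes the narrow sentence as complete.

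Most of this stands, and it limits the finding. A reader might infer that the protocol permits single-method enrolment for these women. The documents do not support that, because the general rule still applies to them. A reader might also infer that the protocol prescribes a class it elsewhere refuses. That holds only on Reading A, and even there a hormonal IUD escapes.

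Nor can the gaps between scheduled pregnancy tests serve as a measure of harm. They are the same for every woman of childbearing potential, with or without this sentence. Appendix 2 (Table 2) disqualifies a subject from study treatment on a positive test, and Section 8.8.1 stops study drug immediately on pregnancy.

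The reply does not remove the defect. The sentence is mandatory in tone, is the only one written for this subgroup, does not refer to the dual-method rule, and names a set that no one can look up. The stated reason for excluding systemic hormonal methods, an unassessed interaction, is not limited to estrogen, so it supports no exception for progestin-only products.

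**Conclusion.** The point holds as an inconsistent instruction: wrong as written, minor in severity. Two parts hold on any reading: one method against two, and a set that is not listed. The conflict over systemic hormonal methods holds on one reading only.

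Few if any of about 60 subjects would be affected. That is a judgement, because the documents do not say how many women on HRT with doubtful menopausal status were expected. The risk assumes a site that treats the more specific sentence as sufficient; nothing in the documents shows that this happened. There is no effect on the analysis. SAP Section 1 records that the sponsor decided in July 2022 to terminate the study and stop developing the drug, so the point matters for the plan as written and for any reuse of this appendix.

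**What to change.** Replace the HRT sentence in Appendix 4 with: *Females on HRT whose menopausal status is in doubt and who wish to continue HRT during the study are considered of childbearing potential and must follow the dual-method rule under Contraceptive Requirements; as for all female subjects, systemic hormonal methods do not count.* Keep the following sentence, which lets a woman stop HRT so that her status can be confirmed.

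This wording adds no new tier of methods and does not make the systemic exclusion depend on HRT use. If the sponsor wants a highly effective tier for these women, it should name the methods itself, because the protocol gives no basis for choosing them.

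The cost is one sentence, matching consent and site-training text, and slightly less choice of method for these women. Sample size, endpoints and analysis do not change.
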